## 4.4.2.4 Abridged 12 week end of observation questionnaire for GP

For each evaluable patient recorded as having been discharged from under the care of the specialist HCP to the care of their GP during the 12 week observation period, their GP will be contacted and invited to complete an abridged end of observation SCEM questionnaire which will gather information on clinical events of medical interest and serious adverse event reports [classified using the International Conference on Harmonisation definitions [36]] reported since date of discharge from secondary care up to end of the 12 week observation period, and recorded within primary care medical charts. Data obtained from this abridged 12 week SCEM questionnaire will include:

- o Anticoagulant treatment regimen as prescribed in primary care
- event reports of selected risks of interest (Table 4)
- cause and date of death (if died);
- reported pregnancies and outcome of birth.
- o date and reasons for stopping (if stopped) including switching
- any newly prescribed concomitant treatments

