## 3.0 ETHICAL CONSIDERATIONS

All studies carried out by at the DSRU will be conducted in accordance with national and international guidelines. [31;32] For this cohort study, ethics approval via IRAS (integrated research application system) in the UK will be required. Participating specialist HCPs will be asked to provide patients with documentation (with a unique study reference code). Patient study documentation will include an patient information sheet about the study which will describe that their secondary care medical charts will be accessed during the time-frame of active study data collection by the specialist HCP and/or DSRU research staff in order to extract exposure and outcome data relevant to the 12 week observation period, \*\*\* and also that their primary care medical charts may be accessed (*contact details to be provided on the consent form*), if they are discharged to the care of their GP within the 12 week observation period. It will also provide contact details of the DSRU study team if they have any questions.

Specialist HCPs will provide patients with a consent form so that patients can consider and give consent for their participation within this project. The consent form will stress confidentiality, that no specific details of their treatment will be released to external parties, that the patient may withdraw consent at any time by contacting either the specialist HCP or the DSRU study research team directly, and that the patient will not be asked to attend clinics more than usual or undergo any additional treatment or questioning. The consent form will also request information to be provided on patient ethnicity, current marital status, current employment status, smoking and alcohol use. This is optional and will be used to inform on representativeness of study cohort. Three signed copies are required. Those patients who wish to inform the DSRU immediately of their decision will give the signed consent form to the specialist HCP. They in turn will send the original to the DSRU, retain one copy for their records and issue a copy to the patient. Where a patient is unable to sign the consent form (e.g. because of weakness of the dominant hand following stroke), consent will be confirmed orally in the presence of a witness (an individual other than the person taking consent) who will sign the consent form on behalf of the participant.

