Period of observation for analyses will commence from index date (i.e. actual start date of anticoagulant treatment, not the date first seen by the specialist) and continue for 12 weeks (or less if patient discontinues to be under the care of the specialist HCP; to be established via the 12 week end of observation questionnaire) in order to allow for detection of outcomes associated with oral anticoagulant treatment initiation as recorded in medical charts. This study will also collect information on exposure to any other medicines (including those given as part of acute care management within the four calendar weeks prior to index date) as recorded in medical charts in order to explore impact of those treatments on outcomes of interest. Since patient care is likely to be shared between secondary and primary care for most patients during the 12 week observation period, the patient's GP will be contacted††† to complete a simple questionnaire to collect any information on outcomes of interest that have been recorded in the patient's medical charts held in primary care during the 12 week observation period to minimise under-reporting on selected outcomes. Where additional outcomes are identified that have not be reported by the initiating prescriber, these will be followed-up with the GP to ascertain further information.

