#### 4.4.1.2 Exposure/outcome data collection

The second phase will also have two parts.

Part 1: At least twelve weeks post index date, the specialist HCP will be prompted to complete a questionnaire which will gather information recorded within medical charts on medical history and medication use prior to or present on index date; changes on general health and medications during treatment, clinical events of medical interest and serious

adverse event reports [classified using the International Conference on Harmonisation definitions [36]]. For patients for whom the specialist HCP reports that the patient was discharged to primary care for continued treatment during the 12 week observation period, the patient's GP will be contacted to complete an abridged end of survey 12 week questionnaire using data recorded within primary care medical charts.

Part 2. Events of interest will undergo aggregate assessment of drug-relatedness, which may include follow-up using event-specific questionnaires sent to the specialist HCP (see 4.4.2.3) or GP. These events will be assessed for drug-relatedness by DSRU staff.[37] With the exception of these enquiries for additional information on selected events, no further monitoring of patients for purposes of data collection for this study from medical charts will occur post the survey period.

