The following relates to Section 2.2.2 secondary objective (iii) Status of indication-related characteristics (alteration of diagnosis, stroke (CHADS2/ CHA2DS2-VASc) and bleeding risk score (HAS BLED) if available) will be summarised, plus pattern of anticoagulant treatment adherence at the end of the 12 week observation period (as estimated from Medication Possession Ratio††††††) will be summarised. The frequency and reasons for attendance to clinics for review and management of anticoagulation and/or acute hospitalisations (including hospital referrals) will also be summarised, where reported. Alterations in treatment programme (change in dose, other drugs) will be described, as will any reason(s) for stopping treatment (including switching) and transition plans to other anticoagulants.

Changes in these indication-related characteristics and treatment details will be examined by comparing values at index and at 12 weeks post index date. Exploratory analysis may include data mining and descriptive measures for describing alterations in treatment programme.

The number of pregnancies, trimester of first exposure and details of births, terminations and miscarriages will be presented. The number of deaths (as recorded in medical charts) in the total cohort for each month of exposure will be calculated. Causes of death will also be described by system-organ class.

Sensitivity analyses will examine any under-reporting using data provided from the patients GP.

Where no. days held will be calculated from information derived from 12 week questionnaire on number of prescriptions and average treatment length of prescriptions (usually given in 7, 14,28,56 day repeats); no. days supply expected will assume chronic use from start to end of study observation or treatment stop date (if stopped)

4.7.5 To quantify the incidence risk and rate of events reported in the 12 week observation period in both the rivaroxaban and contextual cohort and in patient subgroups of special interest.

The following relates to Section 2.2.2 secondary objectives (i) and (iv) regarding a) major bleeding outcomes as specified in the primary objective for the contextual cohort, b) other major or non-major clinically relevant bleeding outcomes not specified in the primary objectives, c) thromboembolism (recurrent and incident) and d) any other events reported in the 12 week observation period.

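### The protocol contradicts itself on who gets the GP form and for which period, so events before discharge and in never-discharged patients have no systematic GP capture

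*Supplement*

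**What the plan says.** Section 4.1 gives the reason for using GP data: "Since patient care is likely to be shared between secondary and primary care for most patients during the 12 week observation period". The GP will therefore be contacted for outcomes of interest held in primary care over the 12 weeks, so as to limit under-reporting. Outcomes that the initiating prescriber did not report are to be followed up with the GP. No discharge condition and no later start date is attached.

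The operational sections are narrower.

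- Section 4.4.1.2 applies the GP form where the specialist reports that "the patient was discharged to primary care for continued treatment during the 12 week observation period".
- Section 4.4.2.4 sends it "For each evaluable patient recorded as having been discharged from under the care of the specialist HCP to the care of their GP" within the 12 weeks, and limits it to events "reported since date of discharge from secondary care up to end of the 12 week observation period".
- Section 3.0 tells patients that their primary care charts may be accessed "if they are discharged to the care of their GP within the 12 week observation period".

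Two sensitivity analyses use these data to look for under-reporting. The one in section 4.7.5 adds GP-recorded events that are confirmed on follow-up, for patients discharged to primary care. The one in section 4.7.4 says only: "Sensitivity analyses will examine any under-reporting using data provided from the patients GP".

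**The concern.** The stated purpose of the GP data is to find outcomes that the specialist's notes lack while care is shared. The form as specified starts after that shared phase for discharged patients, and is never sent for patients who stay with the clinic. Such patients are foreseen: section 1.2 allows outpatient follow-up by the specialist, and section 4.3.2 allows management in secondary care alone.

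Section 5.2 concedes that specialist notes may be incomplete for outcomes outside cardiovascular disease, which would include gastrointestinal and urogenital bleeding. The outcomes most exposed are probably the clinically relevant non-major bleeds in secondary objective (iv)(d). Table 2 defines these partly by unscheduled contact with a physician, who may well be the GP. Risks could be understated, and the planned check has no GP data with which to show it for the uncovered patients and time.

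**Working it through.** **Who is covered, and for when**

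| Source | Patients | Period |
|---|---|---|
| GP contact, section 4.1 | no discharge condition stated | the 12 weeks |
| GP form, section 4.4.1.2 | reported by the specialist as discharged | not stated |
| GP form, section 4.4.2.4 | recorded as discharged | discharge to week 12 |
| GP chart access, section 3.0 | discharged within 12 weeks | the 12 weeks |
| Specialist form, section 4.4.2.3 | evaluable patients with an index form | first 12 weeks |
| Under-reporting check, section 4.7.5 | discharged patients | limited by the GP form it draws on |

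Two cells have no systematic GP data: time before discharge in discharged patients, and all 12 weeks in patients never discharged. The section 4.7.5 check works by adding GP events, so it can add nothing in either cell, however many events sit there.

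**An unsettled boundary.** Section 4.4.2.3 has the specialist form cover the first 12 weeks. Section 4.1 lets observation end sooner if specialist care ends. On the first reading the two forms overlap after discharge; on the second they meet at discharge. The protocol does not say which applies.

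**The trigger.** Under section 4.4.1.2 the GP is approached when the specialist reports discharge. Section 4.1 says that the end of specialist care is established from the specialist's own 12-week form. Section 4.3.2.3 removes a patient from the outcome analyses only when the specialist and GP forms are both blank or missing, so a GP form alone should keep the patient in. No described step generates a GP form when the specialist form is missing.

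**Size.** The documents give no figure for under-reporting. The sample-size figures in section 4.2.1 provide context, using n = 3.84 × p(1 − p) / d².

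- DVT/PE: 3.84 × 0.004 × 0.996 / 0.0039² = 1005.8 (stated 1005).
- AF: 3.84 × 0.007 × 0.993 / 0.0069² = 560.6 (stated 561).

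Both reproduce. Expected primary events are 1005 × 0.004 = 4.0 and 561 × 0.007 = 3.9.

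If a share f of events is missed, the expected estimate is p(1 − f). Taking f from 10% to 50%, purely as an assumption:

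- DVT/PE: 0.40% falls to 0.36% (f = 10%) or 0.20% (f = 50%).
- AF: 0.70% falls to 0.63% or 0.35%.

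Section 4.7.2 does not reject the null hypothesis if observed incidence lies within the precision limits. At the minimum sample sizes the upper limits are 0.40 + 0.39 = 0.79% and 0.70 + 0.69 = 1.39%.

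- DVT/PE: 8/1005 = 0.796% is outside; 7/1005 = 0.697% is inside.
- AF: 8/561 = 1.43% is outside; 7/561 = 1.25% is inside.

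At that boundary, one missed bleed changes the conclusion in the reassuring direction. Away from it, it does not.

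**The case against.** The best reply is that the GP form is not the only route. Hospital charts are open to the specialist and study staff (section 3.0). Charts from other specialties may be examined for selected outcomes (section 5.1). A footnote to section 4.1 expects overlap with M-PEM to limit under-reporting of primary-objective events. The primary outcome is major or intracranial bleeding, and nothing shows that such bleeds would be recorded only in GP notes. This stands against any inference that events in the uncovered time are never captured. It does not close the gap. The specialty charts are optional. The footnote itself warns of GP non-response, and by the Executive Summary M-PEM covers rivaroxaban prescribed by GPs in England, which leaves out Wales, the contextual cohort and hospital-only prescribing.

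A reader might also infer that the two forms share no time window, so that the check cannot run. That is not supported. The specialist form nominally covers all 12 weeks, and the section 4.7.5 analysis adds events, so it needs no overlap. It is also expressly confined to discharged patients, so it misleads only if reported more widely.

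Two further limits stand. The sensitivity analysis in section 5.2 concerns over-reporting, and the one in section 4.7.4 belongs to health profile and treatment changes. Neither is a bleeding under-reporting check.

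Finally, section 4.4.2.4 does not name the 12-week form as the only record of discharge, and section 4.4.3.1 pursues non-returned forms. It would go too far to say that the GP is never approached when the specialist form is missing; the protocol describes no step for it.

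**Conclusion.** The contradiction is established from the text. Section 4.1 promises GP-held outcomes over the 12 weeks; sections 4.4.1.2, 4.4.2.4 and 3.0 make this conditional on discharge, and section 4.4.2.4 starts the event window at discharge. Followed as written, the plan has no systematic GP capture before discharge or in never-discharged patients, and the section 4.7.5 check cannot speak to either.

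Any bias from missed events is downward, most plausibly for clinically relevant non-major bleeds. Its size cannot be derived: neither the share of person-time before discharge nor the share of events held only by GPs is given, and the 10% to 50% range above is illustrative. The missing trigger when the specialist form is absent rests on reading sections 4.1 and 4.4.1.2 together. This should be corrected, but it does not show that the primary estimate is materially wrong.

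**What to change.** 1. Have the GP form cover index date to week 12 for every patient for whom it is sent. This is the cheapest and most useful step: one changed date on a form already planned, and slightly more chart review for the GP.
2. Reconcile sections 4.1, 4.4.1.2, 4.4.2.4 and 3.0 on eligibility, so that the GP is also contacted for shared-care patients, as section 4.1 implies, and when the specialist form is still missing after the one-month reminder. This costs some additional GP forms with the usual fee and a small amendment to the information sheet. Section 1.2 already describes consent to GP contact without a discharge condition.
3. State whether specialist observation ends at discharge or runs to week 12 (section 4.1 against section 4.4.2.3).
4. In section 4.7.5, limit the under-reporting conclusion to the patients and period that both sources cover. This is a wording change only.

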# 4.4.2.5 Follow-up Questionnaires

During the course of the study, selected outcomes of interest (arising from Section 2.2) may undergo further evaluation for aggregate assessment of drug- relatedness to inform on any unusual features/manifestations, relevant risk factors, clinical course and behaviours (see section 4.8). Where necessary, a supplementary follow-up questionnaire which is bespoke to the outcome of interest may gather additional relevant information where recorded within medical charts. [37]

With the exception of these enquiries for additional information on selected events, no further monitoring of patients for purposes of data collection will occur post the survey period. In accordance with Good Pharmacovigilance Practice (GVP) sections VI.C.1.2.1 and VI.C.2.2.2, [38] data will be analysed at aggregate level partially at the time of compiling the interim report (because all information may be available then) and at study completion. Such aggregate analyses can help formulate possible hypotheses which then require further analytic study. Because of the epidemiological nature of the design of this cohort study, any *conclusions* on drug-relatedness will be made on aggregate basis at study milestones, i.e. when the interim and final reports are written (see Section 4.9.2 on Communications).

If any other safety issues become apparent during the conduct of this study, additional events and/or event categories may be added to the list of events for follow up and this will be documented accordingly.

Specific events of interest for further evaluation:

1. Pregnancies: All reported pregnancies will be followed-up using a supplementary questionnaire to describe the outcome of pregnancy§§§§§.

<sup>§§§§§§ Drug-relatedness assessments of abnormal birth outcomes are not conducted by the DSRU

- 2. Deaths: All reported deaths will be followed-up to try to establish the cause of death.
- 3. Events: Selected events of interest as defined in Table 4 may be followed-up for additional information on relevant risk factors, where insufficient information is provided on the questionnaire. The event of switching given as a reason for stopping rivaroxaban (although not defined in Table 4) will undergo further evaluation.
- 4. Adverse events: Other adverse events deemed of medical importance by the DSRU which are considered to be possible safety signals (either arising from literature reports post marketing, or subsequent to interim data analysis) may also be followed-up for additional information on relevant risk factors for signal strengthening purposes.
- 5. Adverse events: Events within the list of Rare and Iatrogenic Adverse Reactions (RAIDAR) compiled by the DSRU (Appendix 2) will be automatically followed up if a more likely alternative explanation for their occurrence is not given.

# 4.4.3 Methods to Maximise Questionnaire Response Rate

## 4.4.3.1 Patient 12 week end of observation questionnaire

A proportion of Specialist HCPs or GPs are likely to fail to submit these questionnaires. Methods to maximise response rates will include prompts from study facilitators by phone, email and personal contact and reminder questionnaires targeted at those who have not responded within one month of the date the initial questionnaire was sent.

# 4.4.3.2 Specific event follow-up questionnaires

A duplicate event follow-up questionnaire will be sent to specialist HCPs or GPs for the specific patient(s) for whom they have not responded to the initial follow-up questionnaire; within six weeks of the date the initial event follow-up questionnaire was sent. Specialist HCPs and GPs will be offered remuneration for each follow-up questionnaire that is completed and returned to the DSRU.

# 4.5 Data processing

Specialist HCP/ GP/patient identifiable information will be stored within a unique database. All original documents and individual correspondence from HCPs will be stored for 15 years at the DSRU, with considerable care taken to preserve patient confidentiality (see below).

# 4.5.1 Review of data

All returned questionnaires with clinical data will be coded onto the study database. Medically important adverse events that have been selected for follow-up will be coded as a priority. There will be a regular monthly review of both the number of patients identified and study questionnaires returned, processed, and classified as void. This will assist in determining the point at which the final cohort size will be achieved. Aggregate data will be reviewed at interim and end of study milestones.

# 4.5.2 Coding of data

Data on indications, exposure, relevant medical history and medication use plus events of interest will be coded directly from targeted closed format questions on the questionnaire (which reference Medical Dictionary for Regulatory Activities (MedDRA) terminology) and coded onto the bespoke study database. Other events reported on the questionnaires as free text will be coded onto this database using the DSRU Event Dictionary Doctor Summary Term synonym list that is mapped to MedDRA, in order to enable consistent reporting to be provided using MedDRA terminology.

Study specific coding procedures will facilitate consistency in coding the data. An SOP will be created upon development of the study specific SCEM database and will be maintained within the DSRU. Regular meetings of DSRU staff will be held to discuss study questionnaires that are difficult to code. A consensus opinion will be reached by medically qualified staff.

Methods to handle issues of missing or conflicting data, will be summarised within the detailed study specific Data Management Plan (DMP) which will be constructed to assist database development and data analysis.

Completed questionnaires will be examined upon receipt for data completeness. Missing data are those where a variable is directly reported as missing or unavailable, where a variable observation is blank, where the reported data may not be interpretable, or where the value

must be imputed to be missing because of data inconsistency or out-of-range results. The individual responsible for completing the questionnaire will be contacted to obtain the missing or correct information and data corrected when possible.

The degree of data completeness will be summarized at interim stage. The distribution of observed variables for patients with missing data will be compared to patients with complete data to gain insight into whether there is any non-random systematic missing information. The most appropriate method to handle missing data for final analysis will be determined by the Project Steering committee at Interim stage.

